### **2.8.3 Handling of missing values/censoring/discontinuations**

#### **MMR rates by specific time points:**

Patients without any documented response for which an evaluable response assessment was never provided will be considered as non-responders for the period of time up to that time point.

**Molecular response category by specific time points:** The category “Missing” will be assigned to patients for whom an evaluable response assessment was never provided.

**Time to MMR:** For patients in the FAS who have not experienced any MMR, the time will be censored as follows in the Kaplan-Meier analysis:

If a patient does not achieve the specified response before the cut-off date for the analysis, censoring time will be the last molecular assessment (PCR) date on treatment prior to the cut-off date or the EoT visit, whichever comes first.

If a patient discontinues study treatment prior to achieving a response for a reason other than disease progression or death, then the patient will be censored at the last molecular assessment (PCR) date on treatment prior to the cut-off date or the EoT visit, whichever comes first.

If a patient discontinues study treatment prior to achieving a response due to progression or death, then the censoring time will be set to the longest follow-up time in the treatment group, that is, consider the response is impossible to reach.

In case no on-treatment response assessment was performed, the patient will be censored at day 1.

[figure not shown]
**Duration of MMR:** For patients who have not experienced any event (loss of MMR, progression to AP/BC, or CML-related death), the duration will be censored at the last molecular assessment (PCR) date on treatment.

[figure not shown]
**PFS:** For patients who have not experienced protocol defined event (disease progression to AP/BC or death from any cause), the patients will be censored at the date of last study assessment (PCR, cytogenetic, hematologic or extramedullary) before the cut-off date.

**OS:** Patients who are alive at the time of the analysis data cutoff date will be censored at the date of last contact (see Section 2.1.1) before the cut-off date.

### **2.8.4 Statistical hypothesis, model, and method of analysis**

There is no formal hypothesis to test in this study.

## **2.10 Interim analysis**

As the primary time point is by 24 weeks, the primary analysis will be an interim analysis. The primary analysis will be performed when the last patient completes 24 weeks of treatment or discontinues early.

As appropriate, annual interim analyses will be planned for publication or any regulatory purpose. No formal interim analysis will be performed. Only summary statistics will be provided.

Final Analysis will be performed when the last patient completes 72 weeks or discontinues early. A final CSR will be written.

## **3 Sample size calculation**

This is an open label, three-cohort study to assess safety and efficacy of study of asciminib (ABL001) monotherapy in patients with chronic myeloid leukemia in chronic phase (CML-CP) previously treated with at least 2 prior TKIs (tyrosine kinase inhibitors) and CML-CP patients harboring the T315I mutation previously treated with at least 1 prior TKIs.

For all CML-CP with the exception of those harboring the T315I mutation, there will be random allocation of patients to eliminate selection bias at the time of cohort allocation. Those patients will be assigned to either Cohort A consisting of asciminib 40 mg BID patients or Cohort B consisting of asciminib 80 mg QD. For CML-CP patients harboring the T315I mutation, they will be assigned to Cohort C with asciminib 200 mg BID, which is the dose required for that patient population. It is worthwhile mentioning that random allocation of patients in cohorts A and B will be pursued for patient selection only. The study is not powered to show differences in Primary and Secondary endpoints between study cohorts.

Primary objective of the study is to assess safety profile of this combination drug during 24 weeks for all cohort patients.

A sample size of 40 evaluable patients for Cohort A is estimated based on a two- sided 95% confidence interval for an incidence rate of an AE using the large sample normal approximation that will extend 0.12 from the observed incidence rate of an AE (precision or margin of error of 12%) for an expected incidence rate of 18%. Considering drop-out rate of 10%, approximately 45 patients will be enrolled for safety assessment for the Cohort A of this study.

Retaining the same assumptions, approximately 45 patients will also be enrolled for Cohort B. Additionally for Cohort C, approximately 25 patients will be enrolled.

Thus, approximately total 115 (45+45+25=115) patients will be enrolled for Cohort A (n1=45) and Cohort B (n2=45) and for Cohort C (n3=25) of the study.

## 4 Change to protocol specified analyses

No change to the protocol specified analysis has been made.

## 5 Appendix

### 5.1 Imputation rules

#### 5.1.1 Study drug

The following rules should be used for the imputation of the dose end date for a given study medication component.

**Scenario 1:** If the dose end date is completely missing and there is no EOT page and no death date, the patient is considered as on-going:

The patient should be treated as on-going and the cut-off date should be used as the dose end date.

**Scenario 2:** If the dose end date is completely or partially missing and the EOT page is available:

- Case 1: The dose end date is completely missing, and the EOT completion date is complete, then this latter date should be used.
- Case 2: Only Year(yyyy) of the dose end date is available and yyyy < the year of EOT date:  
Use Dec31yyyy
- Case 3: Only Year(yyyy) of the dose end date is available and yyyy = the year of EOT date:  
Use EOT date
- Case 4: Both Year(yyyy) and Month (mm) are available for dose end date, and yyyy = the year of EOT date and mm < the month of EOT date:  
Use last day of the Month (mm)
- All other cases should be considered as a data issue and the statistician should contact the data manager of the study.
- After imputation, compare the imputed date with start date of treatment, if the imputed date is < start date of treatment:  
Use the treatment start date

Patients with missing start dates are to be considered missing for all study medication component related calculations and no imputation will be made. If start date is missing then end-date should not be imputed.

#### 5.1.2 AE, ConMeds and safety assessment date imputation

The imputations specified in this section are only used for analyses of time to and duration of AEs and concomitant medications.

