The occurrence of adverse events should be sought by non-directive questioning of the patient (subject) during the screening process after signing informed consent and at each visit during the study. Adverse events also may be detected when they are volunteered by the patient (subject) during the screening process or between visits, or through physical examination, laboratory test, or other assessments. As far as possible, each adverse event should be evaluated to determine:

1. The severity grade (CTCAE Grade 1-5)
2. Its duration (Start and end dates)
3. Its relationship to the study treatment (Reasonable possibility that AE is related: No, Yes)
4. Action taken with respect to study or investigational treatment (none, dose adjusted, temporarily interrupted, permanently discontinued, unknown, not applicable)
5. Whether medication or therapy was given (no concomitant medication/non-drug therapy, concomitant medication/non-drug therapy)
6. Whether it is serious, where a serious adverse event (SAE) is defined as in [Section 10.1.2](#) and which seriousness criteria have been met
7. Outcome (not recovered/not resolved, recovered/resolved, recovering/resolving, recovered/resolved with sequelae, fatal, unknown)

If the event worsens the event should be reported a second time in the eCRF noting the start date when the event worsens in toxicity. For grade 3 and 4 adverse events only, if improvement to a lower grade is determined a new entry for this event should be reported in the eCRF noting the start date when the event improved from having been Grade 3 or Grade 4.

All adverse events should be treated appropriately. If a concomitant medication or non-drug therapy is given, this action should be recorded on the Adverse Event eCRF.

Once an adverse event is detected, it should be followed until its resolution or until it is judged to be permanent, and assessment should be made at each visit (or more frequently, if necessary) of any changes in severity, the suspected relationship to the study treatment, the interventions required to treat it, and the outcome.

Natural progression or deterioration of the malignancy under treatment (including loss of response, progression to accelerated phase or blast crisis and death due to disease progression), will be recorded as part of the efficacy evaluation and should NOT be reported as an AE/SAE.

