### **2.5.3 Handling of missing values**

Missing data for measures of safety will not be imputed.

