### **2.6.1 Adverse events (AEs)**

All the adverse events reported after administration of study drug to 30 days after the last date of drug to the patient are known as treatment emergent adverse events (TEAEs).

The summary tables for adverse events (AEs) will summarize only on-treatment events, with a start date during the on-treatment period (*treatment-emergent* AEs). In addition, a separate summary for death including on-treatment deaths will be provided. All AE will be listed and those collected during the on-treatment period (TEAE) will be flagged.

TEAEs will be summarized by number and percentage of patients having at least one AE in each primary system organ class (SOC) and for each preferred term (PT) using MedDRA coding. A patient with multiple occurrences of an AE will be counted only once in the respective AE category. A patient with multiple CTCAE grades for the same preferred term will be summarized under the maximum CTCAE grade recorded for the event. TEAE with missing CTCAE grade will be included in the 'All grades' column of the summary tables.

In TEAE summaries, the primary system organ class will be presented alphabetically, and the preferred terms will be sorted within primary SOC in descending frequency. The sorting order for the preferred term will be based on their frequency in the ABL001 arm Cohort A.

The following treatment emergent adverse event summaries will be produced by Cohort:

- Overview of TEAEs and deaths

- TEAEs by SOC and PT
- Summary by relationship
- Seriousness
- Leading to treatment discontinuation
- Leading to dose interruption/adjustment
- Requiring additional therapy and leading to fatal outcome

For posting to ClinTrial.gov and EudraCT, a summary table of on-treatment deaths and serious AEs and another summary table of non-serious AEs by treatment, both including occurrences (an occurrence is defined as >1 day between start and prior end date of record of same preferred term) and sorted by SOC and PT, will be presented as well.

All the adverse events will be graphically displayed by Cohorts using bar chart.

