**Table 5-1 Imputation of start dates (AE, CM) and assessments (LB, EG, VS)**

Missing Element	Rule
day, month, and year	
 
• No imputation will be done for completely missing dates
 

day, month	
 
• If available year = year of study medication study medication start date then 
 
◦ If stop date contains a full date and stop date is earlier than study medication study medication start date then set start date = 01JanYYYY
 
◦ Else set start date = study medication study medication start date.
 
 
 
• If available year > year of study medication study medication start date then 01JanYYYY
 
• If available year < year of study medication study medication start date then 01JulYYYY
 

Day	
 
• If available month and year = month and year of study medication study medication start date then 
 
◦ If stop date contains a full date and stop date is earlier than study medication study medication start date then set start date= 01MONYYYY.
 
◦ Else set start date = study medication study medication start date.
 
 
 
• If available month and year > month and year of study medication study medication start date then 01MONYYYY
 
• If available month and year < month year of study medication study medication start date then 15MONYYYY
 

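### The SAP's start-date rule for treatment-emergent AEs admits improvements of pre-dose Grade 3-4 events and leaves AEs with boundary-spanning or missing start dates unclassified

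*SAP*

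**What the plan says.** **Entry to the AE tables.** SAP 2.6.1 says that the AE summary tables "will summarize only on-treatment events, with a start date during the on-treatment period". SAP 2.1.1 runs that period from first administration to 30 days after the last. The SAP gives no other criterion. Protocol 12.7.2 is worded differently: its tables take only events that began or got worse in the on-treatment period. SAP section 4 declares no change to the protocol's analyses.

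**How records are made.** Protocol 10.1.1 has a worsened event entered a second time with the date of worsening. For Grade 3 and 4 events it also requires a new entry on improvement, "noting the start date when the event improved from having been Grade 3 or Grade 4".

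**Incomplete dates.** SAP Table 5-1 has rules for partial AE start dates. If only the day is missing and the month is that of first dose, the start is set to first dose, unless a full stop date comes earlier. The same applies when only the year is known and it is the year of first dose, again unless a full stop date precedes first dose. For fully missing dates the table says: "No imputation will be done for completely missing dates". The introduction to SAP 5.1.2 limits the use of all these rules: "The imputations specified in this section are only used for analyses of time to and duration of AEs and concomitant medications". SAP 2.5.3 adds, for the primary objective: "Missing data for measures of safety will not be imputed".

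**The concern.** The incidence of AEs and SAEs over 24 weeks in Cohorts A and B is the core of the primary endpoint, and the treatment-emergent flag decides which records enter those tables. A rule that looks only at a record's start date can go wrong in two ways.

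- It can admit a record whose date marks recovery, not onset. A patient who got better after starting asciminib would then be shown with a treatment-emergent event.
- It gives no answer when the start date is too incomplete to place on one side of a boundary. The SAP holds a suitable convention in Table 5-1 but does not allow its use for this flag.

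At stake is whether two programmers working from the same SAP would build the same primary tables, and whether those tables follow the protocol's definition.

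**Working it through.** **The plan's own figure.** SAP section 3 bases the cohort size on a "two- sided 95% confidence interval for an incidence rate of an AE using the large sample normal approximation", with an expected rate of 18% and a half-width of 0.12.

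- n = z² × p(1 − p) / d² = 1.96² × 0.18 × 0.82 / 0.12² = 39.37, rounded up to 40.
- With 10% drop-out, 40 / 0.9 = 44.4, rounded up to 45.

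Both stated figures reproduce, and nothing here changes them. At n = 45 the half-width at 18% is 0.112.

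**Improvement records.** Take a Grade 3 or 4 event that starts after consent and before first dose.

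1. It is an AE record, because Protocol 10.1.1 collects AEs from consent. Conditions already present at consent go to medical history and are not affected.
2. The event improves after first dose. Protocol 10.1.1 requires a new record dated at the improvement.
3. That date lies in the on-treatment period, so SAP 2.6.1 counts the record as treatment-emergent.
4. Under Protocol 12.7.2 the event neither began nor got worse on treatment, so it should not be counted.

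The effect is limited. The new record carries the lower grade, so it reaches a Grade 3-or-higher count only when Grade 4 falls to Grade 3. A patient counts once per preferred term, so nothing changes if the patient has another on-treatment event of that term. True worsening is not lost, because it has its own dated record. The only SAP rule that links adjoining records of one preferred term is confined to the registry-posting tables.

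**Incomplete start dates.** The cases separate as follows.

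| What is known of the start date | Status in the incidence tables as written |
|---|---|
| Month and year, or year, wholly inside the on-treatment period and clear of the week limits | On-treatment; no imputation needed |
| Any partial date with a full stop date before first dose | Pre-treatment; no imputation needed |
| Partial date spanning first dose | Undefined; Table 5-1 would set it to first dose |
| Partial date spanning the 30-day limit or the 24-, 48- or 72-week limit | Undefined; Table 5-1 would give a date |
| Completely missing | Undefined; Table 5-1 gives no date either |

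This can also produce an inconsistency. SAP 2.6.2 allows a time-to-first-occurrence analysis for AEs of special interest, where Table 5-1 may be used. One event could be dated on-treatment there and have no status in the incidence table.

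**Scale.** The documents give no count of partially dated AEs or of Grade 3-4 AEs before first dose, so the bias cannot be computed. For scale only, with all 45 patients in the Safety Set, one patient is 1/45 = 2.2 points. In Cohort C it is 1/25 = 4.0 points. Near the design rate:

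| Patients with the event | Rate | Exact 95% CI |
|---|---|---|
| 7/45 | 15.6% | 6.5 to 29.5 |
| 8/45 | 17.8% | 8.0 to 32.1 |
| 9/45 | 20.0% | 9.6 to 34.6 |

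**The case against.** A reader might infer that every AE with a partial start date drops out of the primary tables. The documents do not support that. The SAP nowhere excludes such records; it is silent on them. Many partial dates can be placed without imputation, as the table above shows.

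A reader might also take SAP 2.5.3 as a general ban on imputing dates. It sits under the primary objective and reads naturally as being about missing measurements, and the same SAP does impute AE dates. The limit on imputation rests on SAP 5.1.2 alone. Nor can a count be had by applying an assumed share of incomplete dates to an assumed number of AE records: both inputs would be guesses, and the product would treat every partial date as unclassifiable.

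The strongest case on the other side is that the residue is tiny and already guarded. Missing values are queried (Protocol 11.2). SAEs and data for primary variables are fully source-verified (Protocol 11.3). All AEs are listed, with incomplete dates shown as such. No hypothesis is tested, the design precision is 12 points, and the two gaps may pull in opposite directions. This stands as an argument for low severity.

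It can also be said that SAP section 1 follows the protocol unless otherwise specified, so the protocol's criterion still governs. That does not settle the matter, because SAP 2.6.1 does specify its own rule and gives improvement records no exception.

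**Conclusion.** The concern holds in a narrow form. As written, SAP 2.6.1 counts the improvement of a pre-dose Grade 3-4 AE as treatment-emergent, contrary to Protocol 12.7.2 and with no change declared. Separately, AEs whose start date is completely missing, or spans a boundary, have no defined status in the primary and secondary incidence tables, because SAP 5.1.2 does not extend Table 5-1 to that flag.

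The first gap can only raise the counts. The second has no set direction, since the SAP does not say what happens to the records. Affected records are likely few, though the documents do not allow a count. Each misclassified patient is worth 2.2 points in a cohort of 45, assuming all 45 are in the Safety Set. Severity is low. The sample size is not affected.

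**What to change.** In SAP 2.6.1:

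- Restore the protocol's criterion, so that an AE is treatment-emergent if it began or got worse in the on-treatment period.
- State that a record documenting only the improvement of an AE begun before first dose does not create a treatment-emergent event. A later worsening still counts through its own record.

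In SAP 5.1.2:

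- Extend Table 5-1 to the treatment-emergent flag and to assignment to the 24-, 48- and 72-week periods.
- State a default for completely missing start dates, for example treatment-emergent unless the end date precedes first dose. Other defaults are possible; what matters is that one is written down.

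The cost is a few SAP sentences and light programming to recognise improvement records from grades and dates already collected. No new data are needed. The one downside is that a few ambiguous AEs will be conservatively counted as treatment-emergent.

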**Table 5-1 Imputation of start dates (AE, CM) and assessments (LB, EG, VS)**

Missing Element	Rule
day, month, and year	
 
• No imputation will be done for completely missing dates
 

day, month	
 
• If available year = year of study medication study medication start date then 
 
◦ If stop date contains a full date and stop date is earlier than study medication study medication start date then set start date = 01JanYYYY
 
◦ Else set start date = study medication study medication start date.
 
 
 
• If available year > year of study medication study medication start date then 01JanYYYY
 
• If available year < year of study medication study medication start date then 01JulYYYY
 

Day	
 
• If available month and year = month and year of study medication study medication start date then 
 
◦ If stop date contains a full date and stop date is earlier than study medication study medication start date then set start date= 01MONYYYY.
 
◦ Else set start date = study medication study medication start date.
 
 
 
• If available month and year > month and year of study medication study medication start date then 01MONYYYY
 
• If available month and year < month year of study medication study medication start date then 15MONYYYY
 

**Table 5-2 Imputation of end dates (AE, CM)**

Missing Element	Rule (*=last treatment date plus 30 days not > (death date, cut-off date, withdrawal of consent date))
day, month, and year	
 
• Completely missing end dates (incl. ongoing events) will be imputed by the end date of the on-treatment period*
 

day, month	
 
• If partial end date contains year only, set end date = earliest of 31DecYYYY or end date of the on-treatment period *
 

Day	
 
• If partial end date contains month and year, set end date = earliest of last day of the month or end date of the on-treatment period*
 

Any AEs and ConMeds with partial/missing dates will be displayed as such in the data listings.

Any AEs and ConMeds which are continuing as per data cut-off will be shown as 'ongoing' rather than the end date provided.

### 5.1.2.1 Other imputations

#### Incomplete date of initial diagnosis of cancer

Completely missing dates will not be imputed. Partial dates of diagnosis will be compared to the treatment start date.

- If DIAG year < study treatment start date year and DIAG month is missing, the imputed DIAG date is set to the mid-year point (01JULYYYY).
- Else if DIAG month is not missing, the imputed DIAG date is set to the mid-month point(15MONYYYY).
- If DIAG year = study treatment start date year and (DIAG month is missing OR DIAG month is equal to study treatment start month), the imputed DIAG date is set to one day before study treatment start date.

### 5.2 AEs coding/grading

Adverse events are coded using the latest available version of Medical dictionary for regulatory activities (MedDRA) terminology.

AEs will be assessed according to the Common Terminology Criteria for Adverse Events (CTCAE) version 5.0.

The CTCAE represents a comprehensive grading system for reporting the acute and late effects of cancer treatments. CTCAE grading is by definition a 5-point scale generally corresponding to mild, moderate, severe, life threatening, and death. This grading system inherently places a value on the importance of an event, although there is not necessarily proportionality among grades (a grade 2 is not necessarily twice as bad as a grade 1).

